3.0 Objectives

The purpose of this research is to provide prosthesis prescription guidance for VA clinicians whose patients carry infants, toddlers, and other loads.

The specific aim of this research is to identify the study prosthetic foot that minimizes biomechanical gait deviations when compared to the standard-of-care for veterans with lower limb amputation who carry infants, toddlers, or other loads.

We will conduct a human subject experiment with unilateral transtibial amputees (n=40). Each participant will walk on an instrumented treadmill with no added load and four added load conditions of 13.6 kg: anterior, posterior, intact-side carry, and prosthetic-side carry. Using a

within-subject experimental design with block randomization, each participant will wear: a standard-of-care prosthetic foot, this same prosthetic foot with a heel-stiffening wedge, this same prosthetic foot but one category stiffer, a dual keel prosthetic foot intended for load carriage applications, and a powered ankle-foot purported to adapt to changing loads.

In general, we hypothesize that one of these prosthetic feet will minimize biomechanical deviations for (1) no added load, (2) anterior added load, (3) posterior added load, (4) intact-side carry load, and (5) prosthetic-side carry load.

Our specific hypotheses for each load condition are:

H1 a study prosthesis exists that maximizes the vertical GRF impulse (a measure of body support),

H2 a study prosthesis exists that maximizes the anterior GRF impulse (a measure of body forward propulsion),

H3 a study prosthesis exists that minimizes the peak-to-peak range of sagittal plane whole-body angular momentum (a measure of balance control primarily for anterior and posterior added load conditions),

H4 a study prosthesis exists that minimizes the peak-to-peak range of frontal plane whole-body angular momentum (a measure of balance control primarily for intact-side and prosthetic-side added load conditions), and

H5 a study prosthesis exists that minimizes the mechanical energy expenditure (allow for more efficient locomotion).

4.0 Resources and Personnel

Data collection procedures for this study will be conducted at the VAPSHCS. See Study Staff Sheet attachment for listing of personnel, ability to obtain consent, and access to PHI.

Under the supervision of the PI, designated study staff will be responsible for conducting recruitment, consent and scheduling study procedures. The PI, Investigators, and/or Research Engineers and assistants will conduct procedures with participants. The PI, Investigators, and the Biostatistician will be primarily responsible for data analysis and interpretation; Research Engineers and assistants may also assist with this. Under the supervision of the PI, the Program Coordinator is responsible for IRB related matters.

There are no contractors involved in the data collection procedures for this study.

There are no Data Use Agreements entered into for this study.

5.0 Study Procedures

5.1 Study Design

This study will employ a within-subject experimental design. Each participant will wear, in block randomized order, a standard-of-care prosthetic foot, this same prosthetic foot with a heel-stiffening wedge, this same prosthetic foot but one category stiffer, a dual keel prosthetic foot

intended for load carriage applications, and a powered ankle-foot purported to adapt to changing loads. All study prostheses are commercially available. Each participant, wearing each of the study prostheses, will walk on an instrumented treadmill with no added load and four added load conditions of 13.6 kg: anterior, posterior, intact-side carry, and prosthetic-side carry. The load condition will be presented in block randomized order. The protocol consists of two study visits of no longer than four hours each. A third visit may be needed if data are found to be missing or corrupted, also lasting no longer than four hours.

The anticipated risks of the study include injury to the residual limb (skin irritation or damage) while participating due to wearing the study prostheses (which may be heavier than their as-prescribed prosthesis) or carrying study loads (13.6 kg). Our research prosthetist will discuss any concerns such as low back pain or arthritic joint problems with each participant to determine study suitability and minimize this risk. Some study participants of diabetic/dysvascular etiology may be at risk of injury to the contralateral limb due to carrying study loads. Our research prosthetist will discuss these issues with each participant to establish study suitability. Individual participants in the proposed research are not expected to receive a direct benefit from their participation. The potential benefit of the proposed research is to the veteran lower limb amputee population in general. The anticipated benefit is knowledge of how heel-stiffening wedges, stiffer feet, dual keel prostheses, and powered prosthesis function under varying load conditions. The risks to subjects are low; no life sustaining or life supporting interventions are used as a part of the proposed research protocol. The potential benefit and low risk suggest a favorable risk/benefit ratio.

Individuals with lower limb amputation may also be at a slight risk of injury (e.g., arising from a trip, a fall, or failure of the study prosthesis) or discomfort while they wear the study prostheses. The study prosthesis may have properties that are different than their as-prescribed prosthesis. As per clinical practice, subjects will be instructed to exhibit caution while acclimating to the study prosthesis. This is the same instruction provided when a veteran receives a new prosthetic component as part of a clinical prescription. Subjects will be asked to contact the PI or study staff in the event of any study-related pain or injuries to schedule an examination

The study population will be individuals with unilateral transtibial amputations. We anticipate approaching up to 500 individuals to enroll up to 40 individuals.

Vulnerable populations will not be specifically targeted for enrollment.

This study will not include specimen banking.

5.2 Recruitment Methods

Up to 500 individuals may be approached during recruitment and enrollment procedures. Please note that all references in this section to in-person contact/initial-screening will follow the Screening Script attachment, all references to approach letters and postcards refer to the Recruitment Letter attachment.

Recruitment Activities at the VA

Medical Record/Database: Letter/Phone/In-person

Designated research staff will screen relevant clinic lists in the VA and UW electronic medical record systems (orthopedics, podiatry, orthotics and prosthetics, amputee clinic) to identify potential participants.

After review of relevant clinic lists, designated staff will go to the clinic or contact providers on the phone or via encrypted VA email to ask if a patient might be a good fit for the study. If the clinician agrees that a patient may be an appropriate study participant, during an appointment the clinician will ask the patient if she/he is interested in speaking with designated study staff; patients will be given a chance to opt out. For patients who are interested, designated study staff will speak to potential participants directly after a clinic visit and/or use the electronic medical record system to obtain potential participants' contact information (i.e., name, address, telephone number). For potential participants who learned about the study in person but may not have time to complete the eligibility screening with us, designated study staff may give them a flyer and/or business card and make a follow-up approach phone call and/or send an approach letter. If potential participants are unable to meet with designated study staff in-person then we will send an approach letter.

We may also search the electronic medical record systems to identify individuals who may meet inclusion and exclusion criteria and mail them the approach letter.

If potential participants have not spoken with us between 7 and 14 days of the first call and/or mailing the approach letter, designated study staff will contact them by phone up to two more times (three times total) about this study. The approach letter will also include an "opt out" postcard. The opt-out postcard will have a unique study recruitment identification code. If an individual returns the postcard to opt out, they will not be approached about this study again.

Clinician Referral

Designated staff will inform providers working in relevant clinics about the study and inclusion/exclusion criteria so they can refer potential participants to contact the study team. Flyers and business cards may be provided to clinicians to give to patients that are interested in the study. If a clinician informs patients about the study and the patient agrees to be contacted about it, the clinician may provide us with the patient's name (via encrypted email/in-person/on the phone). We will look up the patient's contact information in the electronic medical record system and make an approach call (in this instance – we will obtain printable documentation from the clinician, via encrypted email or a note in the medical record, that the patient agreed to be contacted on the phone).

Flyers/Text

Flyers may be posted in designated areas at the VA Puget Sound (Seattle and American Lake) on the CCTV system and in publicly accessible locations in the community (e.g., public libraries, community centers, coffee shops). Flyers and study staff business cards will also be posted and distributed to potential subjects at clinics in the community (copies of the letters of support will be submitted to the IRB as miscellaneous submissions, as they are obtained); clinicians and support staff will direct interested individuals to contact us to learn more about the study. The flyers may also be re-sized to be used in print publications or as a complete image in online ads. We may post classified ads in print and online publications. We may also post the classified ad text to our Center's webpage.

VA Puget Sound Center Registry: Letter/Phone

At the VA Puget Sound, designated study staff may also identify potential participants using the VA Center for Limb Loss Prevention and Prosthetic Engineering Subject Registry (PI: [name], #00433). The Registry contains contact information for participants who were screened for and/or participated in previous studies with our research group and agreed to be contacted (via

phone call and/or letter) for future studies. Designated study staff may make an approach phone call and/or send an approach letter to potential participants asking whether they are interested in the study. If potential participants have not spoken with us within 14 days of the first call and/or of the mailing the approach letter, designated study staff will contact them by phone up to two more times. The approach letter will also include an “opt out” postcard. The opt-out postcard will have a unique study recruitment identification code. If an individual returns the postcard to opt out, they will not be approached about this study again. Interested individuals will be screened for eligibility. Designated study staff may also speak with these potential participants in-person if they have an upcoming clinic visit.

Eligibility Screening

Interested individuals will be screened for eligibility in-person or over the phone; see attached screening script.

Recruitment Activities at UW/Harborview

A confidentiality agreement will be obtained for this activity; the UW does not consider itself “engaged” for the recruitment activity described below, please see attached engagement worksheet.

Designated VA study staff may screen relevant UW/Harborview clinic lists, appointment calendars and patient medical records to identify potential participants with a qualifying amputation. Study staff may also attend clinic at these facilities to identify and/or contact potential participants. Before or after clinic, study staff will discuss with the clinician any patients that might be appropriate candidates. If the clinician agrees that the study may be a good fit for a patient, the clinician will ask the patient if she/he is interested in speaking with study staff. For patients who are interested, study staff will speak to potential participants directly during/after a clinic visit to tell them about the study, give them a study flyer, and/or request their permission to screen them for initial eligibility (via the VA IRB approved Screening Script) and provide this information to the VA. If potential participants are screened for initial eligibility in person, study staff will label the noted responses with a recruitment id code and no HIPAA identifiers or sensitive health information will be noted on the form. Study staff will transport the forms to the VA for storage. If patients are interested in learning about the study and/or in doing the initial screening but are unable to meet in person with study staff, we will look up the patients’ contact information in their medical record and contact them on the phone and/or send them the VA recruitment letter (the VA IRB approved letter with VA contact information would be sent per the process described above).

Staff may also search/access UW/Harborview medical records to identify individuals with a qualifying amputation, obtain their contact information (i.e., name, address, telephone number) and mail them the approach letter.

Recruitment Activities in the Community

Clinician Referral

Designated VA staff will send providers working in relevant clinics around the community a clinician approach letter and/or email explaining the nature of the research our Center conducts. If interested, designated study staff will inform providers about specific studies currently recruiting and inclusion/exclusion criteria so they can refer potential participants to contact the study team. Flyers/brochures may be provided to clinicians to give to patients interested in the

study. Clinicians may also provide us (via in-person/on the phone) with the names and contact information of patients they are aware of who may be a good fit for the study, and we will send an approach letter. Designated staff may visit clinics periodically to replenish flyer/brochure supplies and educate clinicians on new studies.

Support Groups

Designated VA staff will send support group leaders an approach email explaining the nature of the research our Center conducts. If interested, designated staff will attend support groups to see if patients are interested in participating in our research. We will give interested patients more information about the study. We will bring flyers/brochures to hand out to interested patients.

Payment to Subjects

Subjects will receive \$50/hour for the first hour of each study visit, then \$30/hour for the rest of each study visit to the VAPSHCS. For subjects traveling 20+ miles one way for appointments (40+ miles total), we will provide compensated mileage rates in accordance with the Veterans Affairs Beneficiary Travel program. This amount may fluctuate. To ensure accuracy, study staff will check to make sure the most up-to-date amount is being used prior to adding travel compensation to total compensation amount. Current mileage rates can be found at https://www.va.gov/HEALTHBENEFITS/vtp/beneficiary_travel.asp. For subjects traveling via ferry for appointments, we will provide full ferry fare compensation. We will not offer compensation for other individuals traveling to the appointment with the participant. To ensure the most up-to-date fares are used, study staff will check the Washington State Department of Transportation ferry fare website (<https://www.wsdot.wa.gov/ferries/fares/>) prior to adding ferry fare compensation to total compensation amount. We will determine if travel compensation is required based on contact information recorded during enrollment. If we determine that a participant is not a good fit for the study and cannot do the procedures, s/he will still be compensated for the first hour of the visit and any applicable travel compensation. Payments will be dispersed in cash or by check; checks will be mailed about 6-8 weeks after the final visit.

5.3 Informed Consent Procedures

A waiver of informed consent and HIPAA authorization will be used for recruitment and screening purposes. A waiver of documentation of consent and HIPAA authorization will be used to retain the preliminary eligibility screening responses (see Screening Script). Informed consent will be obtained prior to enrollment in the study.

The Research Coordinator, the PI, and/or other designated staff, as indicated on the study staff form, will conduct the informed consent process. All study personnel will complete the necessary human subjects protections training per VA policy.

5.4 Inclusion/Exclusion Criteria

Inclusion Criteria:

1. Unilateral transtibial amputee
2. Age 18-70
3. Have been fitted with and used a prosthesis for at least six months
4. Do not use heel stiffening wedges or bumpers in their as-prescribed prosthesis
5. Wear their prosthesis for at least four hours per day
6. Are moderately active by self-report

7. Can be fitted with the study prostheses (prosthetic foot size, stiffness category and build heights)

Exclusion Criteria:

1. Do not have a proper fit and suspension and one cannot be achieved with clinical resources
2. Presence of disorder, pain, or injury other than amputation that interferes with gait

5.5 Study Evaluations

Study Prostheses

Each participant will be fit with four different prostheses: (1) a standard-of-care prosthetic foot, (2) this same prosthetic foot with a heel-stiffening wedge, (3) a dual keel prosthetic foot intended for load carriage activities, and (4) a powered ankle-foot purported to adapt to changing loads. For the standard-of-care prosthetic foot, we will use the Sierra prosthetic foot (Freedom Innovations, Irvine, CA). This prosthetic foot is available in sizes 22 to 31 cm (most VAPSHCS prescriptions are from size 27 to 29 cm), stiffness categories 1 to 9 (most VAPSHCS prescriptions are categories 5, 6, or 7). For adjustment of heel stiffness and roll-over characteristics, the Sierra prosthetic foot comes standard with an optional heel wedge that, when affixed to the heel keel as directed, results in a one category increase in stiffness of the heel keel. We also will use the only commercially available dual keel foot, the Thrive (Freedom Innovations, Irvine, CA). This prosthetic foot is available in sizes 22 to 31 cm and stiffness categories 1 to 9 (note: the stiffness categories of the Sierra and Thrive prosthetic feet are identical). For the powered ankle-foot, we will use the only commercially available powered ankle-foot, the Empower (Otto Bock, Austin, TX). This prosthetic ankle-foot is available with a foot keel in sizes 25 to 30 cm and three body-weight dependent stiffness categories.

Load Carriage

To add anterior and posterior loads, subjects will don a weighted and padded pack fitted with additional straps to secure it to the torso (Classic; Camelbak, Petaluma, CA). The pack will have weights placed inside it so that the total mass is 13.6 kg. To allow the participant to carry the load on the intact- and prosthetic-sides of their torso with their arms, the straps from the padded backpack will be removed or constrained.

Experimental Protocol

The protocol consists of two study visits. A third visit may be needed if data are found to be missing or corrupted from previous study visits. At the first visit, subjects will be screened for inclusion and exclusion criteria and consented. Next, each subject will be asked to walk at their own pace 20 m down a straight hallway while wearing their as-prescribed prosthesis. An average of three trials will be used as a measure of their self-selected walking speed (SSWS). We will also collect subject height, body mass, age, components used in as-prescribed prosthesis, years since amputation, amputation etiology, race, ethnicity, and sex/gender.

The study prostheses will then be fit, in random order, to each participant and aligned by a licensed and certified prosthetist ([name], L/CPO) using standard clinical procedures. We will use a sock and foot cover to blind the participants to the study prostheses when possible (use of the powered ankle-foot will be obvious). Participants will continue to use their existing socket and suspension system, but pylon length will be adjusted as needed to accommodate the study prostheses' build height. Subjects will then be provided with at least 15 minutes to walk

Version 2.5; 5/14/2021 VA Puget Sound IRB Protocol Template – Version: 12/2015 Page 13 of 20

about with no added load and the added load conditions to learn how each study prosthesis performs and feels. Rest breaks will be provided as needed. After the subjects have worn all four study prostheses for all load conditions, the subjects will then don their as-prescribed prosthesis. This will complete the first study visit.

After at least one overnight rest period, we will ask the subjects to return to the laboratory for the second study visit. Subjects will be asked to don body fitting garments, after which sixty-two 14 mm reflective markers will be placed on each subject in locations consistent with a modified version of Vicon's Plug-in-Gait full-body model (Centennial, CO). Anthropometric measures will be recorded for static and dynamic modeling. The Plug-In Gait model will be modified by adding reflective markers at the medial malleolus, medial elbow, and first and fifth metatarsal heads of the feet. The thigh and upper arm segments will be tracked with marker clusters instead of wands. The shank segments will be tracked with markers placed on the fibular head and tibial tuberosity instead of tibial wands. Hip joint centers will be calculated using regression equations based on the inter-ASIS distance of the pelvis.

To help understand how individuals achieve biomechanical performance deviations, we will collect surface EMG data from the primary muscle groups involved in human walking. Specifically, we will shave the skin of the tibialis anterior (TA), medial gastrocnemius (GAS), soleus (SOL), vastus medialis (VAS), rectus femoris (RF), biceps femoris long head (HAM), gluteus medius (GMED), and gluteus maximus (GMAX) of the intact leg along the muscle line of action between the origin and insertion points, and clean it with alcohol to decrease impedance. For the residual limb, we will do the same for the VAS, RF, HAM, GMED, and GMAX. Disposable dual surface EMG electrodes with 2.0-cm spacing will then be applied and connected with a pinch-style terminal to a sensor probe (Noraxon, Inc.) with reference electrode and preamplifier. Each electrode will be held securely in place with Coban (3M, Inc.). Data from the probes will be wirelessly transmitted to a receiver where the data will be processed, synced, and stored in real-time with our existing motion capture system (Vicon, Centennial, CO).

Using the same methods as the first study visit, subjects will be blinded to and fit with each study prosthetic foot in random order. After the first study prosthesis is fit, subjects will walk on our existing instrumented treadmill (AMTI, Watertown, MA) their SSWS determined during the first study visit. In random order, subjects will be asked to walk for one minute with no load and the four added load conditions. Kinematic and kinetic biomechanical data will be collected during each one-minute trial using a 12-camera Vicon system (Vicon, Centennial, CO) and two force plates embedded in the split-belt treadmill. Rest breaks will be provided as needed. After each load condition, we will ask the subject to rate their satisfaction with the functional performance of the study prosthesis using an 11-point Likert scale (0-10) where 0 is defined as completely dissatisfied and 10 as completely satisfied. Subject participation in the study will conclude after they have worn all four study prostheses.

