## Statistical Analysis Plan

Outcome metrics: vertical GRF impulse, anterior GRF impulse, peak-to-peak range of sagittal plane whole body angular momentum (WBAM), and peak-to-peak range of frontal plane WBAM.

Linear mixed effects regression was used to assess differences in biomechanical outcomes (the dependent variable) by foot type for each load by combining all loading conditions in a single model and using a foot type by load condition interaction to estimate means and mean differences in outcomes by foot for each load separately. This model assumes a common variance in outcomes across load and foot. Thus, standard errors for the means will be similar across load and foot. Subject and foot type within subject were considered random effects. Several random effects structures were considered (from subject ID intercept only to a full subject by foot interaction model) with the best model chosen based on likelihood ratio tests. Hypothesis testing for the overall association between outcome and foot type were carried out using conditional F-tests for each load type. For comparison, the Benjamini Hochberg (BH) adjustment was also applied to the F-tests for each model across the 5 load conditions to maintain a false discovery rate of 5%. Hypothesis testing for pairwise differences across feet was carried out using Tukey's method to account for the inflation of the Type 1 error due to assessment of 10 pairwise differences for each load. Analyses were carried out using R 4.2.3 (R Foundation for Statistical Computing, Vienna, Austria) and packages tidyverse, lme4, emmeans and lmerTest.

Outcome metrics: positive net ankle joint work.

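### Foot order and load order are randomised within the data-collection visit, but the mixed models have no order terms, so any fatigue or learning drift shared by participants widens the standard errors of foot differences.

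*Protocol*

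**What the plan says.** Both factors are randomised within participant. Protocol section 5.5 (Experimental Protocol) states that at the second visit "subjects will be blinded to and fit with each study prosthetic foot in random order", and then "In random order, subjects will be asked to walk for one minute", unloaded and under each of the four loads. Section 5.1 adds: "The load condition will be presented in block randomized order". It describes no scheme that balances each foot or load over positions. On duration, section 5.1 says "The protocol consists of two study visits of no longer than four hours each", and it allows a third visit when data are missing or corrupted.

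The protocol includes steps against fatigue and learning. Section 5.5 says "Rest breaks will be provided as needed", requires at least one night between visits, and provides practice on each foot at the first visit: "Subjects will then be provided with at least 15 minutes to walk".

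The protocol model (section 5.6) has prosthesis as the explanatory factor, fitted for each load, with random effects for participant and for participant by prosthesis. The SAP's first model combines the loads, with foot, load and their interaction as fixed effects; for the random part, "Subject and foot type within subject were considered random effects". Likelihood ratio tests choose among random-effects structures. The SAP's joint-work model has the same form. None of these has an order, period or trial-number term, and no check for drift is planned.

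**The concern.** This is a multi-period crossover analysed without period. A participant works through a sequence of feet and, on each foot, a sequence of no-load and 13.6 kg trials. If performance shifts along the sequence through tiring or adaptation, two feet worn by one person differ partly because they were worn at different points in it.

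Under random order this has no preferred direction, so it averages out across participants, but it adds variance to every foot contrast. Drift over foot positions appears as foot-within-participant variation, and drift over load positions appears in the residual. Both enter the standard error of a foot difference within a load. At stake are wider intervals and lower power, in a trial whose weakest stated power is 85%.

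**Working it through.** **1. The plan's own figure.** Section 5.6 gives, for vertical GRF impulse under anterior load, a difference of 16.1 and an SD of 16.0 N*s/kg, 20 subjects, p<0.05, and 85% power. A two-sided paired t-test with zero within-person correlation has SD of the difference √2 × 16.0 = 22.63. The standardised difference is dz = 16.1/22.63 = 0.711, and the noncentral t gives 85.5%. The other three stated powers (99%, 98%, 99%) reproduce as 99.3%, 98.6% and 99.9%. A dz of 0.7 is therefore close to the plan's weakest case. The H1 inputs come from one person, so these powers are only illustrative.

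**2. Variance added by foot order.** Let σ be the within-subject SD of a single foot-load value, so a foot difference has variance 2σ². Assume five feet in random order and linear drift of Tσ from first to last foot.
- Variance of five equally spaced positions on 0 to 1, times T²: T²/8.
- Variance of the difference between two positions drawn without replacement: 2 × (T²/8) × (5/4) = 0.3125 T².
- Relative to 2: 0.156 T².

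| T | Added variance | Effective n (of 20) | Power, dz=0.7, n=20 | Power, dz=0.7, n=40 |
|---|---|---|---|---|
| 0 | 0% | 20.0 | 84.4% | 99.1% |
| 0.5 | 3.9% | 19.2 | 83.0% | 98.9% |
| 1.0 | 15.6% | 17.3 | 78.9% | 98.0% |
| 1.5 | 35.2% | 14.8 | 72.4% | 96.0% |

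Effective n is 20/(1 + 0.156 T²). Power divides dz by √(1 + 0.156 T²).

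**3. Load order.** Load positions on two different feet are independent, so drift of Tσ over the five load positions adds 2 × T²/8 to the variance of a foot difference, or T²/8 relative to 2. With T = 1 for both factors the total is 15.6% + 12.5% = 28.1%.

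**4. Where the drift goes.** A simulation of 20 participants × 5 feet × 5 loads (600 runs per setting) used drift in units of the SD of a foot difference, which is 1.41 times the unit above. Foot drift of 1 unit raised the foot-within-participant variance from 0.24 to 0.41 and left the residual at 0.25. Adding load drift of 1 unit raised the residual to 0.41. Mean bias of the foot contrast without order terms never exceeded 0.012 in absolute value.

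**5. Cost of adjusting when there is no drift.** Foot position varies only between feet within a participant, so it draws on the participant-by-foot stratum: 19 × 4 = 76 df at n=20. Averaged over random orders, foot-contrast variance changes as follows.
- Linear foot-position term: up about 1.3% at n=20 and 0.6% at n=40.
- Four categorical foot-position terms: up about 5.8% at n=20.

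Setting 0.156 T² equal to each n=20 cost gives the break-even drift: T = √(0.013/0.156) ≈ 0.29 for the linear term and √(0.058/0.156) ≈ 0.61 for categorical terms.

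**The case against.** The strongest case against is that no drift is shown. Trials last one minute at a fixed treadmill speed, so 25 of them make 25 minutes of recorded walking. The four-hour limit is a ceiling that also covers markers, electrodes and fitting. With practice, overnight rest and breaks, drift of 1 to 1.5 SD common to everyone may be unlikely. That stands: the benefit depends on a quantity the documents do not give.

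It also stands that adjustment can backfire. Categorical position terms would lower precision for drift below about 0.6 SD; at 0.5 SD, power would be about 82.3% with them against 83.0% without. Fixed position terms remove only the drift participants share; drift that differs between people would be only partly removed.

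Sample size matters too. Section 5.6 calculates power for 20 subjects, while sections 3.0 and 5.1 refer to 40; at 40 the power loss is small. Section 5.5 describes four prostheses where sections 3.0 and 5.1 list five. With four feet the loss is slightly larger.

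A reader might infer that the foot comparisons are biased or the tests invalid. The documents do not support that: order is randomised, and the simulated bias was near zero. A reader might also infer that imbalance over positions is certain. The protocol says block randomised without describing the blocks, so the degree of balance is unknown.

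**Conclusion.** The point holds as a modest, conditional matter of efficiency. The models omit a factor that the design itself creates, and any drift common to participants then widens the standard errors of foot differences. Foot-contrast variance rises by about 4% at 0.5 SD of foot drift, 16% at 1.0 SD and 35% at 1.5 SD. At dz=0.7 and n=20 the power loss runs from about 1 to 12 percentage points; at n=40 it is about 3 points at most. These figures assume five feet, unrestricted random order, linear drift and a two-sided paired comparison at 0.05 without multiplicity adjustment. If drift is below about 0.3 SD, leaving order out costs no more than a linear term would.

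**What to change.** Add two fixed effects to each mixed model: foot position as a linear term, and load position within foot as a linear term. Add a visit indicator for trials repeated at a third visit. Report the two slopes, so that readers can see whether drift occurred.

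The SAP is written in the past tense. If the analyses have already been run, keep the main models as they are and report the adjusted versions as a labelled sensitivity analysis.

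The cost is a sentence of SAP text and two slopes per model, plus the visit indicator where it applies. Conduct does not change, and no new data are needed provided the sequence actually used is kept with each trial. If there is no drift, the linear foot-position term raises foot-contrast variance by about 1% at n=20. Linear terms are preferred to categorical ones, which would cost about 6%.
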